### Exclusion Criteria –both Aims

1. History of functional transplant less than 6 months prior to study
2. Use of anti-inflammatory medications other than aspirin < 325 mg/d
3. Use of immunosuppressive drugs within 1 month prior to study
4. Use of anticoagulant medication
5. History of active connective tissue disease
6. History of acute infectious disease within one month prior to study
7. AIDS (HIV seropositivity is a exclusion criteria only for Specific Aim 1)
8. History of myocardial infarction or cerebrovascular event within 3 months
9. Advanced liver disease
10. Gastrointestinal dysfunction requiring parenteral nutrition
11. Active malignancy excluding basal cell carcinoma of the skin
12. History of ACE inhibitor-associated cough or angioedema
13. Ejection fraction less than 30%
14. Predialysis potassium repeatedly higher than 6.0 mmol/L (confirmed on a repeated blood draw)

15. Anticipated live donor kidney transplant
16. Use of vitamin E > 60 IU/d or vitamin C >500 mg/d
17. Pregnant or breast-feeding
18. History of poor adherence to hemodialysis or medical regimen
19. Inability to provide consent

***Specific Aim 1***

20. Subjects with cardiac pacemaker, artificial heart valve, any metallic implant, permanent tattoo, or any retained foreign metallic bodies will be excluded from the magnetic resonance spectroscopy (MRS) study (Specific Aim 1).
21. HIV infection
22. Albumin levels lower than 3.5 mg/dL.

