**Population**

Adult (18 years or older) patients undergoing MHD or will be considered for the study. Inclusion and exclusion criteria will be the same as specified in section 4B and outlined in detail in Protection of Human Subjects section. During the screening period we will test each dialysis subject for Hepatitis B if it has not been done within 1 month. This is done as standard of care for the dialysis procedure.

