**General protocol**

In a randomized placebo-controlled 2X2 crossover study, subjects will receive either HOE-140 or placebo in the first study day. Prior to the first study day, subjects will report to the VUIIS for a training session for the P-MRS. The first study day will occur at least 2 days but not more than 2 weeks after the training session. Participants will report to the CRC for the study day. HOE-140 (IND # 49,049) or placebo will be infused for 30 minutes prior to the initiation of dialysis at a rate of 100µg/kg/h and at 50 µg/kg/h for the duration of hemodialysis. We have previously found that this dose of HOE-140 blocks the vasodilator effect of bradykinin. The study procedures will be performed in the CRC. Participants will be asked to perform the six-minute walk test, as described in Specific Aim 1. Subjects will then undergo HD in the CRC. Serial blood samples will be collected from the arterial tubing of HD 30 minutes before the beginning of HD, at the beginning of HD, 30 minutes and 1 hour after the initiation of HD, and at the end of HD. The patient will receive the same dialysis treatment prescription as their standard-of-care treatment. The investigator has experience performing this protocol. At the end of HD, patients will remain in the CRC for 2 hours; the last blood samples will be collected and subject will be asked to perform the six-minute walk test again. The subject will be then transported to the VUIIS to evaluate mitochondrial function by P MRS and finally discharged home.

One week later, the participants will return to the CRC for the second study day. The procedures will be the same as on the first study day, receiving the other study medication.

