**Markers of oxidative stress and inflammation**

Variable	Pre- HD	Post- HOE	30 min HD	60-min HD	End HD	120 min post HD
Primary endpoint:						
• Half time of PCr recovery (  P-MRS)						X
Secondary endpoints:						
• Six-minute walk test	X					X
• F2-Isoprostanes	X	X	X	X	X	X

In the blood samples we will measure circulating	• Isofurans	X	X	X	X	X	X
	• Inflammatory cytokines	X	X	X	X	X	X
	• Lactate-to-pyruvate ratio	X	X	X	X	X	X

markers of mitochondrial function (lactate-to-pyruvate ratio), oxidative stress (F2-Isoprostanes and Isofurans) and inflammation. Table 2 summarizes the variables that will be measured in Specific Aim 2. Blood will be centrifuged immediately after collection and stored at -80°C degrees until processing. F2-Isoprostanes and F2-Isofurans are products of lipid peroxidation and markers of oxidative stress. Both will be measured in plasma using negative ion gas-chromatography mass spectroscopy as previously described. Serum IL-1 $\beta$ , IL-6, IL-8, IL-10 and C-reactive protein will be measured using Luminex immunoassay technology. Monocyte chemo-attractant protein 1 concentrations will be measured by ELISA using commercially available kits (Linco Research, St Charles MO).

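### The MRS exclusion in section 4.0 (item 20) is limited to Specific Aim 1, although Aim 2 subjects also have 31P-MRS, on both study days, for the primary endpoint

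*Combined protocol and SAP*

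**What the plan says.** Section 4.0 divides its exclusions in two. Items 1 to 19 stand under "Exclusion Criteria –both Aims". Items 20 to 22 stand under a Specific Aim 1 heading. Item 20 names pacemakers, artificial heart valves, metallic implants, permanent tattoos and retained metal, and says these subjects will be "excluded from the magnetic resonance spectroscopy (MRS) study (Specific Aim 1"). Its scope is therefore given twice, by the heading and by the item's own text.

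For Aim 2, section 6.0 (Population) says: "Inclusion and exclusion criteria will be the same as specified in section 4B and outlined in detail in Protection of Human Subjects section". Under General protocol, subjects first attend the imaging institute for MRS training, and "The first study day will occur at least 2 days but not more than 2 weeks after the training session". On the study day, two hours after dialysis ends, "The subject will be then transported to the VUIIS to evaluate mitochondrial function by" 31P-MRS. For the second study day, "The procedures will be the same as on the first study day, receiving the other study medication". The Aim 2 table of variables lists "Half time of PCr recovery" by 31P-MRS as the primary endpoint, and the Aim 2 sample-size paragraph in section 10.0 does the same.

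Section 7.0 bears on this in two places. Item 7 of the potential risks describes device malfunction, heating of metal and skin irritation with tattoos, and names no aim. The text on protection against risk says patients will be asked about metal devices, tattoos and retained metal. It names no aim either, and does not say what follows if the answer is yes.

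**The concern.** Both aims depend on the same scan, but the eligibility list attaches the scan's exclusion to only one of them. Taken at its word, section 4.0 lets a patient with a pacemaker or metallic implant meet every Aim 2 criterion.

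Two things are at stake. The first is safety: the hazards that section 7.0 describes belong to the scanner and do not depend on the aim. The second is the endpoint: such a patient could be randomised to a treatment order, could receive study drug, and could then supply no primary endpoint. The crossover is planned with only 11 subjects, and the primary comparison is within subject, so each subject needs both scans.

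**Working it through.** **1. Does any criterion for both aims cover MRS?** Items 1 to 19 deal with transplant history, medications, infection, cardiovascular events, liver disease, malignancy, potassium, pregnancy, adherence, consent and similar matters. None concerns implants, metal or tattoos.

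**2. Does the heading set scope?** It does for at least one neighbouring item. HIV infection is item 21, under the same Specific Aim 1 heading, and item 7 of the shared list confirms that "HIV seropositivity is a exclusion criteria only for Specific Aim 1". Item 20 carries the aim label in its own text as well.

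**3. Does Aim 2 use the scan?** It does. The aim is stated in terms of 31P-MRS in section 2.0. The Aim 2 General protocol schedules the scan on both study days. The Aim 2 table and section 10.0 make it the primary endpoint.

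**4. Side by side**

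| | Aim 1 | Aim 2 |
|---|---|---|
| 31P-MRS for the primary endpoint | yes, once | yes, twice |
| MRS training session beforehand | yes | yes |
| MRS hazards described (section 7.0) | yes, no aim named | yes, no aim named |
| Inquiry about metal and tattoos (section 7.0) | yes, no aim named | yes, no aim named |
| Exclusion stated in section 4.0 | yes, item 20 | none |

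The rows agree except the last, and the documents give no reason for that difference.

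**5. Count of scans.** Section 12.0 plans 78 subjects in Aim 1 and 11 in Aim 2.

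- Aim 1: 78 × 1 = 78 endpoint scans
- Aim 2: 11 × 2 = 22 endpoint scans
- Total: 78 + 22 = 100
- Outside item 20's stated scope: at most 22/100 = 22%, or 11 subjects

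Training sessions are not counted. The upper figure assumes that no one takes part in both aims. If all 11 came from the Aim 1 dialysis group of 26, they would already have met item 20 and the count would be 0. The documents do not address overlap, so the range is 0 to 11 subjects and 0 to 22 scans.

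**6. Context: the Aim 2 sample size.** This figure is not disputed. Section 10.0 gives a difference of 0.33 min, an SD of 0.35 under each treatment, a correlation of 0.5 and a two-sided paired t-test at 0.05.

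- SD of differences = √(2 × 0.35² × (1 − 0.5)) = 0.35, as stated
- Power from the noncentral t distribution: 80.4% at n = 11, so the planned 11 reproduces
- At n = 10: 75.6%

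The planned number therefore just reaches 80%, with no spare subject. The n = 10 figure would apply only if an unscannable subject were not replaced. Section 10.0 says drop-outs will be replaced, but does not say whether a subject who cannot be scanned counts as one. No loss of power is claimed here.

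**The case against.** The strongest reply has four parts.

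- **Wording.** Where the authors mean to restrict a criterion to one aim they write the word only, as in inclusion item 4 and exclusion item 7. Item 20 does not, and it is phrased around the procedure, so its label may be a drafting remnant. That is plausible. But a remnant that gives the wrong scope in an eligibility list still needs correcting.
- **Existing safeguards.** The section 7.0 inquiry applies to patients generally and is made in order to avoid MRS risk, which implies acting on the answer. The training visit falls at least 2 days before the first study day. Both make an unsafe scan unlikely, and that part of the objection stands. Neither is an eligibility criterion, however, and the training visit is not described as a screening step. Aim 1 has the same inquiry and its own training session, and still has item 20.
- **Text elsewhere.** The Aim 2 Population paragraph refers to a section 4B and to a Protection of Human Subjects section. Neither label appears as a heading in the supplied document. An MRS criterion for Aim 2 could sit there, so the conclusion is confined to what section 4.0 lists.
- **Consequence.** Section 5.0 does not say when randomisation occurs, so an affected patient might be found before it. This stands too: randomisation of such a patient is possible under the text but is not shown to be likely. The scan count measures the reach of the mismatch, not an expected number of problems.

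**Conclusion.** The concern holds: section 4.0 is wrong as written. The stated scope of its MRS exclusion conflicts with the Aim 2 procedures, with the Aim 2 primary endpoint and with the aim-neutral risk text in section 7.0.

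The mismatch reaches up to 11 subjects and 22 of 100 planned endpoint scans if the two aims enrol different people, and none if all Aim 2 subjects first pass through Aim 1. How many would actually have a contraindication cannot be estimated, because the documents give no prevalence.

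This is a scope error in the eligibility list that should be corrected. It is not evidence that MRS safety screening is absent, and no effect on power or on the results is asserted.

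**What to change.** Reconcile both exclusion lists in section 4.0, the Aim 2 Population and General protocol text in section 6.0, and the risk and protection text in section 7.0, so that the protocol's existing MRS exclusion covers every subject it scans. Moving item 20 to the list for both aims and deleting its aim label would do this. State that it is applied at screening, before the first Aim 2 study day. Link the section 7.0 inquiry to that criterion so that a positive answer has a stated consequence. Correct the Aim 2 cross-reference so that it points to a section that can be found.

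No new clinical rule is needed; the content of the exclusion stays with the sponsor and investigator. The core change is one line, and the inquiry and the training visit already exist. The cost is a somewhat smaller pool of eligible Aim 2 patients, by an amount the documents do not allow one to estimate.

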## **5.0 Enrollment/Randomization**

Subjects will be recruited from the Vanderbilt University Medical Center (including the Vanderbilt Nephrology Clinic and the Vanderbilt Outpatient Dialysis Clinic) the Nashville Veterans Administration (VA) Medical Center, and 10 outpatient hemodialysis units operated by Dialysis Clinics Inc (DCI) and DaVita Clinics. Written advertisements, which give the name and phone numbers of a contact Research Nurse, will be placed on bulletin boards in these locations. In addition, subjects may be informed of the study by their dialysis nurse or primary care provider. Subjects who call for more information will be given a brief description of the study protocol and, if interested, will be invited to set up a meeting with the Research Nurse. During this meeting, the Research Nurse or Investigator will describe the study protocol in detail. Interested subjects will be invited to read and sign an IRB-approved consent form and will be given a copy of that consent form.

Subjects will be randomly assigned to treatment order using a permuted-block randomization algorithm (for Specific Aim 2). The Vanderbilt Investigational Pharmacy will be responsible for the storage, preparation, and labeling of all investigational agents and for maintaining accurate drug storage and dispensing logs at Vanderbilt. A Clinical Research Pharmacist, will devise standard operating procedures for the pharmacy to follow with regard to preparing, labeling, blinding, and dispensing study drug.

## **6.0 Study Procedures**

**Specific Aim 1: Test the hypothesis that mitochondrial function worsens with the progression of CKD and initiation of HD**

### ***Population***

Three different groups of patients will be evaluated: 1. Patients with ESRD and on MHD for at least 6 months, 2. Patients with CKD stages 3-5 (eGFR less than 59 mL/min per 1.73 m^2) not yet on MHD and who have visited a nephrologist at least 1 month prior to enrollment, and 3. Control subjects with no CKD. The subjects in each group (including the controls) will be matched by age, sex, race, diabetic status, and BMI. All participants will be adults 18-75 years of age.

### General protocol

After obtaining informed consent, the investigators will perform a physical examination.

### Physical Activity

We will measure physical activity using triaxial accelerometer. For this purpose, the monitor of the size of a small pager is clipped on clothing over the right hip. Activity will be recorded during waking hours. Physical activity will be examined over a 7-day period requiring at least 5 days of recorded activity to be included in the analysis. The accelerometer will provide information about total energy expenditure and energy expenditure of activity.

Prior to any study procedure, subjects will report to the VUIIS for a training session for the  $^{31}\text{P}$  magnetic resonance spectroscopy ( $^{31}\text{P}$ -MRS) as described below. Mitochondrial function will be evaluated using  $^{31}\text{P}$ -MRS. Endurance will be also evaluated using the six-minute walk test as explained below. The subjects will report to the Vanderbilt University Institute of Imaging Science (VUIIS) in the morning on one of the non-dialysis days. During this day we will perform the six-minute walk test and a training session for the  $^{31}\text{P}$ -MRS. Two days later, subjects will be asked to return to the General Clinical Research Center (CRC) at Vanderbilt in the morning under fasting conditions for blood sampling,  $^{31}\text{P}$ -MRS, and skeletal muscle biopsy of the vastus lateralis (see below).

### $^{31}\text{P}$ Magnetic Resonance Spectroscopy

Mitochondria function can be evaluated using non-invasive techniques such as  $^{31}\text{P}$ -MRS, which evaluates the concentration of PCr and other phosphate-energy carrier molecules in limb muscles. [name] and [name], faculty members of the VUIIS, have successfully implemented this technique that will be used to evaluate *in vivo* mitochondrial function. Each subject will lie prone for approximately 30 minutes with a coil positioned over the belly of the vastus lateralis muscle. The position of the coil will be confirmed using scout localizer images and a reference positioned within the center of the coil (Figure 7A). After basal measurements, subjects will be asked to perform cycles of knee extension and rest. Measurements will be recorded during the exercise protocol and for additional 15 minutes (recovery period). Spectra will be used to calculate concentrations of inorganic phosphate (Pi), PCr, adenosine triphosphate (ATP). The primary end-point will be the half-time of PCr recovery (time to achieve half of basal concentration during the recovery period). A spectra obtained by the investigators is shown in Figure 7B. This method is reliable and reproducible and has been considered the “gold standard” to measure mitochondrial function. Subjects will report for an initial familiarization session (a non-dialysis day). During this session, subjects will be familiarized with the exercise protocol. The subjects will be asked to return 2 days later to

[figure not shown]

Figure 7 - A. MRI of the thigh. The white dot above the thigh marks the center of the  $^{31}\text{P}$  MRS coil and aids in positioning the coil over the vastus lateralis (\*). B.  $^{31}\text{P}$  MRS spectra acquired at rest from the vastus lateralis of a healthy 37 y.o. female.

perform the P-MRS. During the 2 days prior to testing, we will ask that subjects 1) perform no moderate or heavy intensity exercise within 1 day of testing; 2) not consume alcohol within the 1 day prior to testing; 3) not consume caffeine or use tobacco within 6 hours prior to testing; and 4) do not eat a meal 3-6 hours before testing.

### **Six-minute walk test**

This test will be performed as previously described. Briefly, patients will be instructed to walk during 6 minutes on a 20 meter corridor. The distance in meters will be recorded. Patients will not be encouraged to perform the test, but they will be able to judge the time remaining from the large clock in the corridor. In this specific aim the test will be performed in a non-dialysis day. [name] (co-mentor of the PI) has standardized the test in his lab and shown that physical activity is lower on dialysis days.

### **Muscle biopsies**

Biopsies will be obtained from the vastus lateralis skeletal muscle. Patients receiving anticoagulant medication will be excluded. Aspirin will be discontinued for 14 days before the procedure. This procedure will be performed under aseptic conditions and local lidocaine anesthesia in the CRC at Vanderbilt, by percutaneous needle biopsy. After removing subcutaneous fat, biopsies will be divided in 3 pieces, one will be immersed in fixatives for electron microscopy; the other 2 pieces will be immediately frozen in liquid nitrogen and stored at -80 °C for DNA and RNA isolation and for future studies (e.g. mitochondrial proteomics). The PI has already completed 5 biopsies in patients undergoing chronic HD.

### **Transmission electron microscopy to assess mitochondrial mass and morphology**

Muscle biopsies will be dissected and cut into small pieces and fixed in glutaraldehyde (4%) and paraformaldehyde (2%) for 2 hours at room temperature. Samples will be prepared for electron microscopy as previously described. Briefly, samples will be post-fixed in osmium tetroxide (1%) for 1 hour, dehydrated and embedded for further sectioning. Thin (80 nm) fiber transverse sections will be stained with uranyl acetate and lead citrate and examined with a transmission electron microscope. Mitochondrial volume density (% of muscle fiber volume occupied by mitochondria) will be determined using a standard point counting method. Representative electron micrographs from patients with ESRD and obtained by the PI are shown in Figure 6.

Table 1. Variables measured in Specific Aim 1

Variable	Specimen
Primary end-point:	
• Half time of PCr recovery (  P-MRS)	Non-invasive
Secondary end points:	
• Six-minute walk test	Non-invasive
• Mitochondrial volume density	Muscle biopsy
• Mitochondrial biogenic factors	Muscle biopsy
• Mitophagy factors	Muscle biopsy
• Lactate-to-pyruvate ratio	Plasma

### **Markers of mitochondrial biogenesis and mitophagy**

Markers will be measured using quantitative RT-PCR in skeletal muscles biopsies. For this purpose, muscle tissue will be homogenized and RNA isolated using RNeasy® Fibrous Tissue Mini Kit RNA (Qiagen, Chatsworth, CA), according to the manufacturer's protocol. Mitochondrial biogenic factors will include PPAR gamma coactivator 1-alpha (PGC-1α), nuclear respiratory factors (NRF) 1 and 2, and mitochondrial transcription factor A (TFAM). Among the mitophagy markers we will evaluate autophagy gene 8 (ATG-8 or LC-3), 5 (ATG-5) and 7 (ATG-7), BCL-2/adenovirus interacting protein 3 (BNIP-3) and BNIP-3 like protein (BNIP-3L). After performing RNA reverse transcription, PCR analyses will be performed in triplicate, using SYBR Green and 18S rRNA as the calibrator

housekeeping gene. Fluorescence signal will be detected using ABI PRISM 7500 Sequence Detection System.

**Lactate-to-pyruvate ratio**

Lactate-to-pyruvate ratio in blood samples has been used as another marker of mitochondrial function. Blood samples will be obtained and mixed with 8% perchloric acid (3 to 1 volume to volume ratio). Lactate will be measured using a colorimetric method (Sigma-Aldrich). Pyruvate will be measured using high performance liquid chromatography (HPLC). Table 1 summarizes the variables that will be measured in Specific Aim 1.

**Specific Aim 2: Test the hypothesis that endogenous bradykinin promotes mitochondrial dysfunction in patients undergoing chronic HD.**

**Population**

Adult (18 years or older) patients undergoing MHD or will be considered for the study. Inclusion and exclusion criteria will be the same as specified in section 4B and outlined in detail in Protection of Human Subjects section. During the screening period we will test each dialysis subject for Hepatitis B if it has not been done within 1 month. This is done as standard of care for the dialysis procedure.

**General protocol**

In a randomized placebo-controlled 2X2 crossover study, subjects will receive either HOE-140 or placebo in the first study day. Prior to the first study day, subjects will report to the VUIIS for a training session for the P-MRS. The first study day will occur at least 2 days but not more than 2 weeks after the training session. Participants will report to the CRC for the study day. HOE-140 (IND # 49,049) or placebo will be infused for 30 minutes prior to the initiation of dialysis at a rate of 100µg/kg/h and at 50 µg/kg/h for the duration of hemodialysis. We have previously found that this dose of HOE-140 blocks the vasodilator effect of bradykinin. The study procedures will be performed in the CRC. Participants will be asked to perform the six-minute walk test, as described in Specific Aim 1. Subjects will then undergo HD in the CRC. Serial blood samples will be collected from the arterial tubing of HD 30 minutes before the beginning of HD, at the beginning of HD, 30 minutes and 1 hour after the initiation of HD, and at the end of HD. The patient will receive the same dialysis treatment prescription as their standard-of-care treatment. The investigator has experience performing this protocol. At the end of HD, patients will remain in the CRC for 2 hours; the last blood samples will be collected and subject will be asked to perform the six-minute walk test again. The subject will be then transported to the VUIIS to evaluate mitochondrial function by P MRS and finally discharged home.

One week later, the participants will return to the CRC for the second study day. The procedures will be the same as on the first study day, receiving the other study medication.

